7.2.14 Definition of Overdose

Overdose, as defined for this protocol, refers to CC-90009 dosing only. On a per dose basis, an overdose is defined as the following amount over the protocol-specified dose of CC-90009 assigned to a given subject, regardless of any associated adverse events or sequelae:

• 10% over the protocol-specified dose

On a schedule or frequency basis, an overdose is defined as anything more frequent than the protocol required schedule or frequency.

Complete data about drug administration, including any overdose, regardless of whether the overdose was accidental or intentional, should be reported in the case report form. Refer to Section 10 for the reporting of adverse events associated with overdose.

7.2.15 Dosage Modifications for Concomitant Use of Strong CYP3A4 Inhibitors in Part B Dose Expansion

In Part B, dosage modification of CC-90009 based on concomitant use with a strong CYP3A4 inhibitor (See Section 8.2 for list of example CYP3A4 inhibitors) will be as follows:

- For 3.0 mg Days 1-7 cohort, reduce CC-90009 dose to 2.0 mg
- For 2.4 mg Days 1-7 cohort, reduce CC-90009 dose to 1.5 mg

Resume the CC-90009 dosage that was used prior to concomitant use of a strong CYP3A4 inhibitor 3 days after discontinuation of the inhibitor.

No dose modification is required for concomitant use of moderate CYP3A4 inhibitors.

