1.2.3.1 Study CC-90009-AML-001

Enrollment of subjects in Part A Dose Escalation of the study has been completed and a total of 72 subjects were treated. (One subject, in the 3.6 mg with dexamethasone premedication cohort, was reenrolled under a new subject number after discontinuing from study and subsequently relapsing after 8 months of complete remission. The subject's two subject numbers were consolidated, and they were counted only once.) All treated subjects had R/R AML. To date, 4

dosing schedules of CC-90009 have been explored; once daily dosing on Days 1-5 of a 28-day cycle (0.3 mg to 4.5 mg), Days 1-7 of a 28-day cycle (3.6 mg), Days 1-10 of a 28-day cycle (3.0 mg), and Days 1-3 and 8-10 of a 28-day schedule (3.0 and 3.6 mg). Dose levels of 3.6 mg and above and the 3.0 mg dose level on the Days 1-10 schedule included premedication with dexamethasone for subjects enrolling starting with Protocol Amendment 5. As of 01 Apr 2021, enrollment in Part A of the study has been completed. After a review of Part A data, the SRC recommended that CC-90009 be dosed at 3.6 mg on Days 1–5 with dexamethasone premedication in Part B Dose Expansion in both R/R AML and R/R HR-MDS. After review of initial data from Part B Dose Expansion with an observation of a higher rate of sepsis in the Part B R/R AML cohort as compared to R/R AML cohorts in Part A, the SRC recommended to close R/R AML and R/R HR-MDS cohorts receiving CC-90009 at 3.6 mg Days 1–5 for enrollment, and two new dose levels (2.4 mg and 3.0 mg on Days 1-7) were recommended to be expanded as part of a dose optimization and sepsis mitigation strategy.

As of the 13 Aug 2021 cutoff date, preliminary data are available for 80 subjects with R/R AML and 2 subjects with R/R HR-MDS. Of the 82 subjects treated with CC-90009, 79 (96.3%) had discontinued from treatment and out of these, 76 (92.7%) had discontinued from the study. The most common reason for treatment discontinuation was progressive disease in 24 (29.3%) subjects. The most common reason for study discontinuation was death in 67 (81.7%) subjects.

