The categorical term of sepsis includes AE preferred terms of bacterial sepsis, Escherichia sepsis, Klebsiella sepsis, neutropenic sepsis, sepsis, sepsis syndrome, septic shock, and Stenotrophomonas sepsis. Twenty-four (29%) subjects experienced sepsis in this study: 18 (25%) subjects were in Part A and 6 (75%) subjects were in Part B in the R/R AML cohort. No sepsis was reported in the 2 subjects enrolled in the R/R HR-MDS cohort in Part B. The rate of sepsis in the Part B R/R AML cohort (75%, 6 of 8 subjects) was higher than the overall rate (25%, 18 of 72 subjects) of sepsis from Part A Dose Escalation of this study, and it was higher than the rate (18%, 2 of 11 subjects) of sepsis among subjects receiving the same dose of CC-90009 on the same schedule in Part A. In Part A, the incidence of sepsis is 15%, 29% and 36% among subjects receiving consecutive daily CC-90009 doses of 2.4 mg and below (n = 13), 3.0 mg (n = 24), and 3.6 mg and above (n = 25), respectively, demonstrating a potential dose-dependent relationship between CC-90009 and the development of sepsis. There was no sepsis reported in cohorts with

CC-90009 dosed at shorter step intervals (ie, when CC-90009 is dosed on cycle Days 1-3 followed by Days 8-10), and this schedule is not being pursued based on a lack of objective responses.

An exploratory analysis of CC-90009 plasma exposures in subjects who developed sepsis showed that exposures were elevated by approximately 1.56-fold compared to subjects who did not develop sepsis. Additionally, subjects who received strong inhibitors of CYP3A4 enzyme (N=20) showed that exposures were elevated by approximately 1.8-fold (median dose-normalized AUC₂₄ = 192 ng.hr/mL) compared to subjects who did not receive strong CYP3A4 inhibitors or received moderate CYP3A4 inhibitors (N = 59, median AUC₂₄ = 106 ng.hr/mL), suggesting a potential drug-drug interaction of CC-90009 with strong inhibitors of CYP3A4.

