Comprehensive analysis of available PK, PD, efficacy, safety, and tolerability data led to the development of a strategy to reduce the risk of sepsis. The strategy includes evaluating doses of CC-90009 lower than 3.6 mg and schedules longer than 5 days that had been selected as the dose level for the Part B Dose Expansion. New Part B R/R AML and R/R HR-MDS cohorts will be enrolled at CC-90009 dose levels of 2.4 mg Days 1-7 and 3.0 mg Days 1-7. The strategy also includes dose reduction of CC-90009 for subjects receiving concomitant strong CYP3A4 inhibitors.

Please refer to the CC-90009 IB for additional PK summary parameters by individual dose levels and for more detailed information concerning the available pharmacology, toxicology, drug metabolism, clinical studies, and AE profile of CC-90009.

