1.3.4 Rationale for Dose and Dosing Schedule in Part B Dose Expansion

Data generated from Part A Dose Escalation of the study suggest a manageable safety profile and encouraging preliminary clinical activity of CC-90009 in subjects with R/R AML (Section 1.2.3). At the completion of Part A Dose Escalation, a total of 72 subjects were treated with CC-90009. Preliminary safety and efficacy data are available for these 72 subjects treated in Part A. All data were assessed both internally and by SRC, and a non-tolerated dose (NTD) was successfully determined on 3 of the 4 schedules evaluated. The Days 1-3/8-10 schedule was not pursued further due to lack of efficacy prior to declaring either a maximum tolerated dose (MTD) or NTD. Based

on the observed DLTs and definitions of NTD and MTD set in the protocol, the SRC declared 3.0 mg Days 1-5 without dexamethasone premedication and 3.6 mg Days 1-5 with dexamethasone premedication as MTDs on the Days 1-5 schedule. After further review of preliminary safety, anti-leukemic activity and PK/PD data from all dose levels, the SRC recommended 3.6 mg Days 1-5 with dexamethasone premedication as the dose and schedule to be expanded for the initial cohorts of R/R AML and R/R HR-MDS subjects in Part B.

Overall, evidence of anti-leukemic activity (decreases in bone marrow and/or peripheral blasts) was seen in subjects treated with CC-90009 at 1.2 mg and above with a trend to deeper and more sustained reductions at the highest dose levels. Objective responses were observed in cohorts with 5 or more days of continuous dosing at 3.0 and 3.6 mg with a trend for better efficacy at 3.6 mg. A higher dose of 4.5 mg on this schedule was not tolerated.

Attempts to shorten the dosing schedules with intermittent dosing of either 3.0 mg or 3.6 mg on Days 1-3 and 8-10 were unsuccessful due to lack of efficacy. While these regimens were tolerated, they were not pursued based on lack of objective response: this intermittent dosing schedule did not sufficiently suppress leukemic blasts, which increased in the peripheral blood on non-dosing days.

Dosing schedules with more than 5 consecutive days (3.6 mg Days 1-7 and 3.0 mg Days 1-10) were not well tolerated at dose levels tested based on DLTs using the current hypotension grading in Protocol Amendment 7 (Table 12), interruptions and missed doses. However, responses were noted in both of these dose levels.

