After an initial 8 R/R AML subjects enrolled in Part B at dose level 3.6 mg Days 1-5 with dexamethasone premedication, a high rate of sepsis (75%) was observed in this cohort, and enrollment to both R/R AML and R/R HR-MDS cohorts were paused. There were no significant findings on demographic and baseline characteristics of R/R AML subjects enrolled at the same dose level (CC-90009 3.6 mg D1-5 with or without dexamethasone premedication) in Part A Dose Escalation (n = 11) and Part B Dose Expansion (n = 8). In both Parts A and B, preliminary analyses of pharmacokinetic data demonstrated increased CC-90009 exposure (1.56-fold) among subjects who developed sepsis as well as increased exposure (1.8-fold) among subjects who received concomitant strong CYP3A4 inhibitors. Preliminary modeling of exposure-sepsis and exposureclinical response relationships indicated that cumulative exposure of CC-90009 (AUC_{CUM}) was less predictive of sepsis than daily exposure (odds ratio [95% confidence interval]: 2.55 [1.17-6.65] for AUC_{CUM} as the predictor vs. 3.84 [1.35–13.35] for AUC₂₄ as the predictor) and that AUC_{CUM} was more predictive of clinical response than AUC₂₄ (odds ratio [95% Confidence Interval]: 5.06 [1.61–21.16] for AUC_{CUM} vs. 3.04 [0.97–13.07] for AUC₂₄). Comprehensive analysis of available PK, PD, efficacy, safety, and tolerability data led to the development of a strategy to reduce the risk of sepsis. The strategy includes evaluating doses of CC-90009 lower than 3.6 mg and schedules longer than 5 days that had been selected as the dose level for the Part B Dose Expansion. New cohorts in Part B will be enrolled at CC-90009 dose levels of 2.4 mg Days 1-7 and 3.0 mg Days 1-7. R/R AML and R/R HR-MDS subjects will be pooled in each cohort with 6 to 40 subjects enrolled in each cohort, including up to 20 subjects with R/R AML and up to 20 subjects with R/R HR-MDS in each cohort. The strategy also includes dose reduction of CC-90009 for subjects receiving concomitant strong CYP3A4 inhibitors. The new Part B cohorts will enroll subjects in parallel. Up to 6 subjects per cohort will be initially enrolled as a safety run-in. The SRC will assess tolerability of the dose and schedule for these initial subjects that completed at least one cycle of study treatment based on the Part A stopping criteria (Section 7.2.8) and recommend further expansion of one or more cohorts. The expanded cohort(s) will be monitored for the excess toxicities including sepsis utilizing the non-binding Bayesian stopping criterion on a continuous basis (Section 9.9.3). Subjects of R/R AML and R/R HR-MDS enrolled in the expansion cohorts will be pooled for analysis of safety, PK, and PD. The SRC will continue to review safety and preliminary efficacy data regularly throughout the study and make recommendations about study continuation, cohort continuation, and dose modification, as appropriate.

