3 OVERALL STUDY DESIGN

3.1 Study Design

Study CC-90009-AML-001 is an open-label, Phase 1, dose escalation and expansion, first-in-human clinical study of CC-90009 in subjects with relapsed or refractory AML (Appendix B) or in subjects with relapsed or refractory higher-risk MDS (Appendix E and Appendix G). The dose escalation part (Part A) of the study will evaluate the safety and tolerability of escalating doses of CC-90009, administered intravenously, and determine the MTD of CC-90009. In Part A, two formulations were tested. The expansion part (Part B) will further evaluate the safety and efficacy of CC-90009 administered at or below the MTD in selected expansion cohorts of up to approximately 20 evaluable subjects in each disease indication (R/R AML and R/R HR-MDS) in order to determine the RP2D. One or more dosing regimens may be selected for cohort expansion (at a minimum, one in R/R AML and one in R/R HR-MDS). MDS subjects will only be enrolled during Part B. Parts A and B will consist of 3 periods: Screening, Treatment, and Follow-up. Leukemia response will be determined by the Investigator. Disease assessment will be based on the International Working Group (IWG) Response Criteria in AML (Cheson, 2003; refer to Appendix C). MDS response will be based on the IWG Response Criteria for Myelodysplasia (Cheson, 2006; refer to Appendix F).

Screening Period

The Screening Period starts 28 days prior to first dose of CC-90009. The informed consent document (ICD) must be signed and dated by the subject and the administering staff prior to the start of any other study procedures. All screening tests and procedures must be completed within the 28 days prior to the first dose of CC-90009.

Treatment Period

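### Table 35 omits the Cycle 1 last-dose PK that Table 8 requires for the Part B Days 1-7 cohorts, and nothing commits the SRC to use those data to check the strong-CYP3A4-inhibitor dose

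*Combined protocol and SAP*

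**What the plan says.** **Sampling.** Section 6.5.1 sends Part B sites to Table 8 for the 2.4 mg and 3.0 mg Days 1-7 cohorts. Its first block applies one set of time points to both Cycle 1 Day 1 and the Cycle 1 last dose, ending 24 hours after the infusion. Cycles 2 to 4 have pre-dose samples only, on the last two dosing days. Table 35 in Appendix N is the Cycle 1 table of events for these cohorts. Its blood PK row is marked on D1 (footnoted as multiple samples) and D2, with nothing on D7 or D8.

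**Strong inhibitors.** From an exploratory analysis, Section 1.2.3.1 reports that "subjects who received strong inhibitors of CYP3A4 enzyme (N=20) showed that exposures were elevated by approximately 1.8-fold"; Section 1.3.4 repeats the figure. Section 7.2.15 then directs: "For 3.0 mg Days 1-7 cohort, reduce CC-90009 dose to 2.0 mg". The 2.4 mg cohort goes to 1.5 mg. Section 8.2 asks sites to avoid strong inhibitors where they can.

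**Part A.** Of the longer schedules, Section 1.3.4 says: "3.6 mg Days 1-7 and 3.0 mg Days 1-10) were not well tolerated at dose levels tested based on DLTs". It adds that the DLTs were judged under the study's own hypotension grading, and it also cites dosing interruptions and omissions. Section 1.2.3.1 lists 3.6 mg as the only dose tried on Days 1-7. Of the sepsis mitigation behind Amendment 9, it says: "The strategy includes evaluating doses of CC-90009 lower than 3.6 mg and schedules longer than 5 days".

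**The concern.** Site staff schedule blood draws from the table of events. If they follow Table 35, Part B has no post-dose profile after Days 1-2. The last-dose profile is the one that shows exposure after a week of daily dosing, and the only Cycle 1 profile that can reflect an inhibitor started after Day 1.

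The reduced dose of 2.0 mg depends on how large the interaction is. The protocol has one estimate, from a non-randomized comparison of 20 subjects with 59, and this trial is the natural place to check it. The plan allows for general PK review, but no section commits anyone to compare strong-inhibitor users with other subjects while the rule is in force.

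**Working it through.** **1. The schedules side by side (Cycle 1 blood PK)**

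| Cohort | Sampling table | Table of events |
|---|---|---|
| Part B, Days 1-7 | Table 8: Day 1 and last dose, each to 24 h (Days 2 and 8) | Table 35: D1, D2 |
| Part B, Days 1-5 (closed) | Table 44: Day 1 to 24 h | Table 6: D1, D2 |
| Part A, Days 1-7 | Table 40: Days 1, 3, 4 and last dose | Table 33: D1, D2, D3, D4, D7 |

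Table 6 agrees with Table 44. Table 35 shows the same D1-D2 pattern but should agree with Table 8, and does not. Table 33, on the same Days 1-7 schedule, does mark D7 (though not D8).

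Table 8 lists 10 time points per profile for intensive sampling and 4 for sparse. With about 10 intensively sampled subjects in a full cohort of 40, the most that could be lost is 10 x 10 + 30 x 4 = 220 samples per cohort, if every site followed Table 35 and every subject reached the last dose.

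**2. The plan's ratio.** Median AUC24 is 192 with a strong inhibitor and 106 without (Section 1.2.3.1): 192/106 = 1.81, which reproduces the stated 1.8. The reference group includes users of moderate inhibitors.

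**3. Where 2.0 mg lands**, assuming dose-proportional AUC24 (Section 1.3.4 says only that exposure rises with dose):

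- Equivalent dose = reduced dose x ratio = 2.0 x 1.8 = 3.6 mg a day (3.62 at 1.81).
- Against the cohort's dose: 3.6/3.0 = 1.20.
- Without the rule: 3.0 x 1.8 = 5.4 mg. The rule removes 1 - (3.6 - 3.0)/(5.4 - 3.0) = 75% of the excess.
- Other ratios: 1.5 gives 3.0 mg, 1.6 gives 3.2 mg, 2.0 gives 4.0 mg.
- The 2.4 mg cohort: 1.5 x 1.8 = 2.7 mg, below both 3.0 and 3.6 mg.

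**4. Uncertainty of the ratio.** The documents give no spread, so assume log-normal AUC24 with log-SD 0.3 to 0.6. For a ratio of medians, SE(log) = SD x 1.2533 x sqrt(1/20 + 1/59) = SD x 0.324. The approximate 95% interval is 1.50-2.19 at SD 0.3 and 1.24-2.65 at SD 0.6. Doubled, these are 3.0-4.4 and 2.5-5.3 mg-equivalent.

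**5. How comparable the Part A benchmark is.** Strong-inhibitor use in the Part A 3.6 mg Days 1-7 cohort is not reported. If the overall share applied (20/79 = 25%, an assumption), mean exposure there was 3.6 x (1 + 0.253 x 0.811) = 4.34 mg-equivalent. Then 3.62/4.34 = 0.83, so 2.0 mg with an inhibitor would sit about 17% below that cohort.

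**6. What the SRC could learn.** At 25% use, each run-in of 6 has 1.5 users, so about 3 of 12 across both cohorts. Comparing geometric means for 3 against 9, SE = SD x sqrt(1/3 + 1/9) = SD x 0.667. Around a ratio of 1.8 the 95% interval is 1.22-2.66 at SD 0.3 and 0.82-3.94 at SD 0.6. If both cohorts fill (20 against 60) and are combined with the earlier 20 against 59, SE = SD x sqrt(1/40 + 1/119) = SD x 0.183, giving 1.62-2.00 and 1.45-2.23.

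**The case against.** **The table mismatch is clerical.** The Table 35 row points to Section 6.5, where Table 8 states the requirement. The Day 1 profile already yields AUC24 for anyone then on an inhibitor, and Table 36 keeps the pre-dose samples on D6 and D7 from Cycle 2. Table 35 as read also repeats several safety rows, so a lost mark is possible. Much of this stands: the sampling is specified, and a reader who inferred that no last-dose PK was planned would be wrong. But the pointer exposes the conflict without removing it. D7 marks for dosing, ECG and marrow survive in the same table, so a dropped PK mark is not the likelier explanation. It should still be confirmed on the published PDF.

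**Safeguards exist.** Section 7.2.8 has the SRC review PK regularly, Table 3 lists PK covariates as exploratory, Section 8.1 allows repeat PK when medication changes, and Section 9.9.1 permits a population analysis. The safety run-in and the Bayesian sepsis monitoring also apply. These keep the point modest, but none commits to the comparison.

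**Stronger readings that the documents do not support:**

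- A reader might infer that 2.0 mg breaks Section 3.1, which describes "CC-90009 administered at or below the MTD in selected expansion cohorts". That sentence concerns the dose administered, and 2.0 mg is below the cohort's own 3.0 mg. Section 7.2.15 never claims to match exposure.
- A reader might infer that inhibitor users will fail to tolerate treatment, or develop sepsis, as at 3.6 mg Days 1-7. Step 5 shows that the equivalence is only nominal. The Part A finding rested on DLTs under the hypotension grading and on disrupted dosing, and Section 7.2.6 excludes Grade 3 or higher infection from DLTs.
- A reader might argue sepsis risk from the cycle total, set against the closed Days 1-5 regimen. Section 1.3.4 reports cumulative exposure as less predictive of sepsis than daily exposure (odds ratios 2.55 and 3.84) and more predictive of response.

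**Conclusion.** Tables 8 and 35 conflict on Cycle 1 PK for the Part B Days 1-7 cohorts, and the operational one is incomplete. This should be fixed. The finding depends only on the table marks being as read.

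The strong-inhibitor dose adds to the reason for fixing it. At the protocol's one exploratory ratio, and with dose proportionality assumed, 2.0 mg is a partial correction: about 3.6 mg-equivalent a day, 20% above the intended 3.0 mg. A true ratio of 1.5 would remove the excess, and the data cannot exclude that at the spreads assumed. Whether partial correction is right is a benefit-risk choice for clinical pharmacology and the SRC, since exposure also predicts response. The documents contain no error in the dose, and neither a replacement dose nor a printed rationale is required. What is missing is a commitment to look at the data that could confirm or revise it.

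**What to change.** 1. In Table 35, add D7 (multiple samples) and D8 (24-hour sample) to the blood PK row, to match Table 8. This is one table row, with no samples beyond those Table 8 already requires.
2. In Section 9.9.3 or 7.2.8, add a sentence: at the run-in review and at later meetings the SRC compares dose-normalized AUC24 in strong-inhibitor users with that in other subjects, pooling the two dose cohorts, and confirms or revises the reduced dose. The cost is a small descriptive analysis. With about three users it will be imprecise at run-in, so it should be presented as descriptive and updated as users accrue. There will be fewer users if sites follow Section 8.2.

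Neither change needs extra patients.

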7.1.2 Formulation

Celgene Corporation will supply CC-90009 clinical drug product as a lyophilized powder for reconstitution to solution in single-use vials and it should be stored per the product label. The drug product is available in two different formulations: Gen 1 and Gen 2b. The study will initially employ Gen 1 (DL1: 0.3 mg, DL2: 0.6 mg, and DL3: 1.2 mg), and then during dose escalation, Gen 2b was introduced at DL4 (2.4 mg) to replace the Gen 1 formulation. Each vial of Gen 1 CC-90009 contains 1.05 mg of CC-90009, 18.6 mg anhydrous citric acid, 18.5 mg anhydrous sodium citrate, and 252.0 mg of Kleptose[™] hydroxypropyl beta-cyclodextrin (HPBCD) as a freeze dried powder. CC-90009 is slightly hygroscopic. Each vial of Gen 2b formulation of CC-90009 contains 1 mg CC-90009 and 800 mg hydroxypropyl-beta-cyclodextrin (HPBCD) as a freeze dried powder. CC-90009 clinical drug product is packaged in a 20 mL US Pharmacopeia (USP) Type I glass vial or local equivalent. The CC-90009 vial does not contain any preservative and is for single use only. CC-90009 should be prepared according to the package instructions, the CC-90009 Pharmacy Manuals, and local practice regulations. Gen 1 formulation is reconstituted in sterile Water for Injection (SWFI). Gen 2b formulation is reconstituted in 0.45% sodium chloride (half strength normal saline) and further diluted in 0.9% sodium chloride (normal saline) for injection (eg, for infusion doses between 0.6 and 10 mg, Gen2b formation is reconstituted with 4.5 mL of 0.45% sodium chloride [half strength normal saline] to a concentration of 0.2 mg/mL The reconstituted solution can be further diluted in 0.9% sodium chloride [normal saline] to achieve a 50 mL volume.)

DMA is a process solvent used during manufacture of Gen 1 formulation of CC-90009 that is removed during processing. The daily dose of DMA residual solvent in Gen 1 CC-90009 must not exceed the ICH permitted daily exposure limit (10.9 mg/day) to proceed with dose escalation above a CC-90009 daily dose of 2.4 mg. Gen 2b CC-90009 was developed to enable doses above the limits imposed on Gen 1 formulation. Gen 2b CC-90009 is permitted at doses up to 20 mg CC-90009 per day. The SRC determined the dose cohort for introduction of Gen 2b CC-90009 during Part A of the study to be DL4: 2.4 mg on Days 1-5.

Females of childbearing potential and fertile males should not handle or administer CC-90009 unless they are wearing gloves.

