7.2.9 Permitted Study Drug Adjustments

Dose reductions are permitted in any cycle, including Cycle 1. Dose reductions that occur in Cycle 1 during dose escalation will constitute DLT as outlined in Section 7.2.6, but subjects will be allowed to continue on CC-90009 at a reduced dose.

When a dose reduction is indicated, the CC-90009 dose from the next lower dose cohort will be selected or a less frequent dosing schedule after discussion with the Medical Monitor. Subjects will dose reduce using the same formulation to which they are currently assigned (eg, Gen 1 CC-90009 \rightarrow Gen 1 CC-90009 and Gen 2b CC-90009 \rightarrow Gen 2b CC-90009). Two dose reductions are allowed. Once the dose has been reduced, it can be escalated when toxicity reaches Grade ≤ 1 . If toxicity recurs at the higher dose, the dose will be reduced a second time, but no re-escalation is then permitted. If any subject continues to experience unacceptable toxicity after two dose reductions (one for the starting dose), CC-90009 will be discontinued permanently.

Intra-subject dose escalation of CC-90009 is not permitted during Cycle 1, but escalation to a dose subsequently deemed to be tolerated in a higher dosing cohort may be permitted in later cycles if approved by the SRC.

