Concomitant use with a strong CYP3A4 inhibitor increases CC-90009 exposure, which may increase CC-90009 toxicities, including the risk of sepsis. Avoid concomitant use of CC-90009 with strong CYP3A4 inhibitors if possible. Alternative treatments for anti-fungal prophylaxis or medication (eg, micafungin, caspofungin, or amphotericin) should be considered. If concomitant use of strong CYP3A4 inhibitors is unavoidable during study treatment, CC-90009 dose reductions are required (Section 7.2.15) and subjects should be monitored closely for signs of toxicities. Subjects can resume CC-90009 at the dose used prior to initiation of the concomitant strong CYP3A4 inhibitor 3 days after discontinuation of the inhibitor.

• Examples of strong CYP3A4 inhibiting medications: Atazanavir, boceprevir, clarithromycin, cobicistat, conivaptan, danoprevir/ritonavir, darunavir, elvitegravir/ritonavir, indinavir, itraconazole, ketoconazole, lonafarnib, lopinavir/ritonavir, mibefradil, mifepristone,

nefazodone, nelfinavir, paritaprevir/ritonavir combinations, posaconazole, ritonavir, saquinavir, telaprevir, telithromycin, tipranavir/ritonavir, troleandomycin, voriconazole

Concomitant use with a strong or moderate CYP3A4 inducer may decrease CC-90009 efficacy. Avoid concomitant use of CC-90009 with strong or moderate CYP3A4 inducers. Alternative treatments with less CYP3A4 induction should be considered.

- Strong CYP3A4 inducers: avasimibe, carbamazepine (Tegretol[®]), enzalutamine, mitotane, phenytoin (Dilantin[®]), rifampin (Rifadin[®]), St. John's wort
- Moderate CYP3A4 inducers: bosentan, efavirenz, etravirine, modafinil, nafcillin

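### The cohort-keyed strong-inhibitor doses in 7.2.15 do not fit the toxicity-reduction rules: a 2.4 mg-cohort subject already on 1.2 mg is told to reduce to 1.5 mg

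*Combined protocol and SAP*

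**What the plan says.** Section 7.2.15 (Part B only) gives one inhibitor dose per cohort: "For 3.0 mg Days 1-7 cohort, reduce CC-90009 dose to 2.0 mg" and "For 2.4 mg Days 1-7 cohort, reduce CC-90009 dose to 1.5 mg". Section 8.2 asks sites to avoid strong inhibitors but, where use is unavoidable, says that "CC-90009 dose reductions are required (Section 7.2.15) and subjects should be monitored closely for signs of toxicities". For the return, 7.2.15 says "Resume the CC-90009 dosage that was used prior to concomitant use of a strong CYP3A4 inhibitor 3 days after discontinuation of the inhibitor"; 8.2 repeats this in permissive form.

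Toxicity reductions are governed elsewhere. Under 7.2.9, "the CC-90009 dose from the next lower dose cohort will be selected or a less frequent dosing schedule after discussion with the Medical Monitor". "Two dose reductions are allowed". After a first reduction the dose may go back up once toxicity is Grade 1 or less. If toxicity recurs at the higher dose, "the dose will be reduced a second time, but no re-escalation is then permitted". The hypocalcemia rule in 7.2.13.2 restarts drug at the next lower dose and offers no schedule alternative.

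Section 7.1.2 lists the first dose levels as "DL1: 0.3 mg, DL2: 0.6 mg, and DL3: 1.2 mg", with DL4 at 2.4 mg. No cohort between 1.2 and 2.4 mg is named anywhere.

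For the Part B run-in, Section 3.1 applies the 7.2.8 criterion (DLT in 2 or more of up to 6 evaluable subjects). DLT evaluability is defined in 7.2.3 as 80% of the planned Cycle 1 dose, with 6 or more doses as the Days 1-7 example.

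**The concern.** Section 7.2.15 is written as if every subject who starts an inhibitor is on the full cohort dose. It says nothing about a subject already reduced for toxicity, or reduced for toxicity while on the inhibitor. Sections 7.2.9 and 7.2.13.2 in turn do not mention the inhibitor doses. Where the rules meet, a site can be told to reduce to a higher dose, or to restore a dose that another section bars.

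Inhibitor dose reduction is named in 1.2.3.1 and 1.3.4 as part of the strategy to lower sepsis risk, adopted after 6 of 8 Part B R/R AML subjects had sepsis. An instruction with that purpose should give one answer for each subject who can reach it. The gap also touches reporting: 7.2.14 defines overdose as 10% over the subject's protocol-specified dose, and it is unclear which dose that is for a subject on 1.2 mg who starts an inhibitor.

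**Working it through.** **1. Figures the plan states.** Exposure ratio with strong inhibitors (1.2.3.1): 192/106 = 1.81, matching the stated 1.8-fold. Minimum doses under the 80% rule: 0.80 x 7 = 5.6, so 6 doses on Days 1-7. The same rounding gives 4 of 5, 8 of 10 and 5 of 6, all as in 7.2.3.

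**2. Subject already reduced for toxicity.** Inputs: inhibitor doses 1.5 and 2.0 mg (7.2.15); next cohort dose below 2.4 mg = 1.2 mg (inferred from DL3 and DL4 in 7.1.2); next below 3.0 mg = 2.4 mg.

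- 2.4 mg cohort, reduced once to 1.2 mg: 1.5/1.2 = 1.25, a 25% increase under an instruction to reduce.
- 3.0 mg cohort, reduced once to 2.4 mg: 2.0/2.4 = 0.83, a genuine reduction. No reversal.

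**3. Resumption, case by case.**

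- Both toxicity reductions before the inhibitor: the pre-inhibitor dosage is already the reduced one. No conflict.
- First toxicity reduction during inhibitor use: 7.2.9 allows later escalation once toxicity is Grade 1 or less. Section 7.2.15 does not repeat that condition, so the passages are incomplete but can be followed together.
- Reduced once, re-escalated, inhibitor started, toxicity recurs, second reduction during inhibitor use: 7.2.9 bars re-escalation, while 7.2.15 orders the pre-inhibitor dosage. Both cannot be followed.

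Section 7.2.9 ends treatment permanently if unacceptable toxicity continues after two reductions. Whether the inhibitor step counts as one of the two therefore matters, and no passage says.

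**4. Frequency.** Earlier TEAE-led reductions: 3 subjects of 82 (1.2.3.1). Earlier strong-inhibitor use: 20 of 20 + 59 = 79. If the two are independent and the rates persist, subjects with both in a 40-subject cohort:

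40 x 3/82 x 20/79 = 0.37.

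The percentage printed beside the 3 is 4.2%, which is 3/72 and not 3/82. With 72 the result is 0.42. Doubling either rate in the 82-based figure gives 0.74; doubling both gives 1.5. The conflicts in steps 2 and 3 are subsets of this overlap.

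**5. The 80% rule for inhibitor users in the run-in.** Seven inhibitor-adjusted doses are 7 of 7 by count. As milligrams of the cohort dose:

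- 2.4 mg cohort: 7 x 1.5 = 10.5 of 7 x 2.4 = 16.8 mg, 62.5%.
- 3.0 mg cohort: 7 x 2.0 = 14.0 of 7 x 3.0 = 21.0 mg, 66.7%.

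A subject with a DLT is evaluable on either reading. Only DLT-free users are affected, so the number of DLTs observed in the subjects already enrolled is the same both ways.

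**The case against.** The 1.2 mg step is an inference. DL3 was given on Days 1-5 as Gen 1, whereas 7.2.9 requires the subject's own formulation and also allows a less frequent schedule after discussion with the Medical Monitor. That stands as a limit: the conflict need not arise every time. It does not close the gap. Section 7.1.2 describes Gen 2b preparation for doses from 0.6 to 10 mg, so 1.2 mg is feasible in that formulation, and 7.2.13.2 reaches the next lower dose with no schedule option.

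Three stronger readings are tempting and are not supported.

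- *Resumption and the bar on re-escalation conflict in general.* They collide only when the second, barring reduction happens during inhibitor use.
- *A 3.0 mg-cohort subject on 2.0 mg could be sent up to 2.4 mg by a toxicity reduction.* This is strained, because 7.2.9 asks for a lower dose.
- *Inhibitor users distort the run-in decision, or say less about the nominal dose.* The Protocol Summary, 7.2.3 and 7.2.12 all express the Days 1-7 rule as a count. Replacement of non-evaluable subjects is written for dose escalation, and the run-in text has its own condition of completing one cycle. On the documents' exposure ratio, 2.0 x 1.81 = 3.6 mg and 1.5 x 1.81 = 2.7 mg, so exposure at the reduced doses is not expected to fall below that of the cohort dose without an inhibitor.

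A reader might also infer harm to the Efficacy Evaluable population from the wording about scheduled dose or doses. Completing one cycle satisfies that treatment requirement without the 80% limb, and the Treated Population is primary.

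**Conclusion.** The concern holds in a narrow form and is minor. As written, 7.2.15 and 8.2 give a 2.4 mg-cohort subject already on 1.2 mg an instruction to reduce that raises the dose by 25%. They also leave one resumption sequence impossible to follow, and the count of reductions is undefined.

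The result rests on 1.2 mg being the dose next below 2.4 mg. The size, about 0.4 subjects per 40, rests on earlier reduction and inhibitor rates persisting and being independent. Section 8.2's advice to avoid strong inhibitors would lower it; higher exposure in users could raise it. The reason to act is the safety purpose of the instruction, not its expected frequency. The run-in evaluability point is a clarification of wording; no effect on the expansion decision is shown.

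**What to change.** Reconcile 7.2.15 and 8.2 with 7.2.9 and 7.2.13.2. The text should say how the inhibitor rule applies to a subject already below the cohort dose, and how a toxicity reduction is made while a subject is on the inhibitor dose. It should also say which passage governs resumption after a reduction made during inhibitor use, and whether the inhibitor step counts toward the two permitted reductions. No dose or clinical rule is proposed here.

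As a smaller clarification, state in 7.2.3 or 7.2.8 that for the Part B run-in the 80% rule is applied by number of doses, as its examples already show. DLT-free inhibitor users are then not dropped while users with a DLT are kept. Show the SRC the run-in DLT count with and without inhibitor users.

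The cost is amendment wording and one extra line in the SRC tables. Dose and concomitant-medication data are already collected, and no subjects are added.
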